17.13 CASE REPORT FORM (CRF) COMPLETION

All CRFs must be completed as per training. The header information at the top of each CRF must be complete and accurate. The monitor will check the visit schedule to ensure that the required CRFs have been completed. The monitor shall check all CRFs for appropriate initials and/or signatures and verify that they can be found on the delegation of duties log. The site and monitor should refer to the CRF completion instructions, to assist them in decreasing queries and the manner in which the CRF forms should be completed.

17.14 EARLY TERMINATION DOCUMENTATION

Any subject who discontinues study treatment early must have the reason documented in the source document and a termination form must be completed.

17.15 MANAGING POOR PERFORMING OR NON-COMPLIANT SITES

If a site is not conducting the study per protocol or Clinical Trial Directive, ICH guidelines or GCP regulations, the monitor should discuss this with SerenaGroup®. If the non-compliance impacts directly on the safety of subjects, study endpoints or timelines, the medical monitor should be involved in the discussion. Corrective action (e.g. extra training,) should be considered. Repeated poor performance may result in the site being shut down.

17.16 FRAUD AND MISCONDUCT

Suspicion that any data provided may not be valid should be reported immediately to SerenaGroup® and the medical monitor.

Examples of trends that may cause suspicion of fraud include but are not limited to:

- Similar handwriting on CRF/source documentation to documentation completed by subjects such as consent forms or quality of life questionnaires.
- No original source documents only copies.
- No adverse events.
- Perfect data with no issues such as missed visits etc.
- A pattern of data for a given site which does not match the pattern of data generated at other sites (adverse events, trends in lab data, repetition of data, and frequency of withdrawals).
- Visit adherence schedule too exact for all subjects.

19 APPENDICES

19.1 ANKLE-BRACHIAL INDEX (ABI)

Technique: Place the patient in the supine position, with the arms and legs at the same level as the heart, for a minimum of 10 minutes before measurement

Select an appropriately sized blood pressure cuff for both the ankle and the arms (figure 1); the cuff width should be, at a minimum, 20% greater than the diameter of the extremity. The ankle cuff should be placed on the leg between the malleolus and the calf. Enough room should be left below both cuffs to permit placement of the ultrasound gel, so that the Doppler device can adequately detect the brachial, dorsalis pedis, and posterior tibial arteries.

Obtain the brachial systolic pressures of both arms. Use the higher of the arm pressures in the ABI calculation. Obtain the pressure in the dorsalis pedis and posterior tibial arteries for the extremity with the target ulcer. Use the highest pressure for the ABI calculation.

Ankle-Brachial Index = Highest ankle pressure/Highest brachial pressure.

Care should be taken to cover the ulcer during the ABI measurement. In addition, patients should be informed that they may experience discomfort during the test secondary to the pressure exerted by the cuff in the area of skin breakdown.

© Mayo Foundation for Medical Education and Research. All rights reserved.

19.2 TIME TRADE OFF EVALUATION

A time-tradeoff (TTO) measurement using an electronic system called Wound-Trade© will be elicited from patients to facilitate the assessment of cost-effectiveness (cost-utility). Value for improving patient quality of life is typically quantified using cost-utility analysis. A cost-utility analysis is defined as a type of cost-effective analysis that compares different procedures and outcomes relative to a person's quality of life. It is the most sophisticated form of economic analysis and typically incorporates utility values. Utility values measure the preference for a health state and range from 0.0 (death) to 1.0 (perfect health). When the change in utility measures conferred by a health care intervention is multiplied by the duration of the benefit, the number of quality-adjusted life-years (QALYs) gained from the intervention is ascertained. This methodology incorporates either the improvement in quality of life and/or length of life, or the value, occurring as a result of the intervention. In wound care, patients' experiences of living with wounds are dominated by symptom management, with all studies showing that the wound and its treatment have a profound effect on quality of life.

WOUND-TRADE©

Wound-Trade© is a system developed and created by [name], MD, Associate Professor, Department of Medicine, Washington University School of Medicine, St. Louis, Missouri and [name], MPH, Health Economist and Epidemiologist, Global Health Economic Projects, LLC, Clifton Park, New York. [name]© is implemented on a laptop computer, which facilitates the development of customized utility interviews. The automated format facilitates a consistent presentation of questions and enables a discounted, risk-adjusted, quality of life health utility index score through classic time-trade-off methodology. An individual is given a hypothetical choice: he/she can live for x-years in perfect health followed by death, or he/she can live y years with a particular chronic condition such as a chronic wound, where $y > x$. The number of healthy years x is then varied until the person is indifferent between the two outcomes. The health utility index in this example equals x/y . For example, suppose that an individual feels that fifteen years of perfect health is worth twenty years of life with a chronic wound. Using the time trade-off approach, this individual is giving a chronic wound a health utility index of 0.75. The health utility index can be used in a cost-utility equation (cost-effectiveness based on quality-adjusted life years) from a new medical treatment or technology:

$$\frac{\text{Cost}_{\text{new}} - \text{Cost}_{\text{old}}}{\text{No. of QALYs}_{\text{new}} - \text{No. of QALYs}_{\text{old}}}$$

RISKS

There are no risks to the patient related to their health or well-being. The scenarios in Wound-Trade© are imaginary and do not interfere with their current therapy as guided by the hospital wound center.

INTERVIEW TIME

The interview process can take as little as a few minutes to 15 minutes to complete. A research assistant will be available to assist the patient with process but will not influence the decisions made by the patient.

WOUND-TRADE SCREEN SHOTS AND INTERVIEW PROCESS

A. Introductory Screen

Researcher will enter the following information:

1. Enter a patient number in subject identifier field;
2. Enter birth date as month/day/ year exactly like this: 06/25/1955;
3. Select either M for Male or F for Female;
4. For the remainder of information it is not necessary to enter it but you can if you wish;
5. Hit continue button to go to next page

The screenshot shows a software window titled "Interview". At the top, it says "Research Associate: Please" followed by four buttons: "Restart", "Suspend", "Go Back", and "Continue". The main area contains several form sections:

- Subject identifier:** A text input field.
- Demographics:** Includes fields for Birthdate, Sex (radio buttons for M and F), Race, Marital, Ethnicity, Education, and Employment, each with a dropdown menu.
- MailingAddress:** Includes fields for Street, City, State, Zip, and Nation (set to USA).
- Contact information:** Includes fields for Tel, Fax, and Email.
- Social:** A list of social settings with corresponding numbers: Home (1), Hospital (2), Nursing home (3), Assisted living (4), Wound clinic (5), Volunteer (7), Other (8), and Not Applicable (0).
- Selections:** A large empty text area.

B. Comorbidities

6. Check all that apply and hit continue:

[figure not shown]
The screenshot shows a software window titled "Interview" with a sub-header "Comorbidities". Below the header, it says "Check all that apply." followed by a list of medical conditions, each with a checkbox:

- AIDS (not just HIV positive)
- Myocardial infarction (history, not just EKG change)
- Congestive heart failure
- Peripheral vascular disease (incl AA>6cm)
- Dementia
- Chronic pulmonary disease
- Connective tissue disease
- Peptic ulcer disease
- Moderate or severe renal disease
- Leukemia (acute or chronic)

[figure not shown]
At the bottom of the window, there are two buttons: "Go Back" on the left and "Continue" on the right.

6. Check all that apply and hit continue:

[figure not shown]
- D. Introductory Patient Screens
 - 1. Hit continue button;

- 1. Patient will read and then hit continue button;

1. Patient will read and then hit continue button;

1. Patient will read and then hit continue button;

The screenshot shows a window titled "Interview" with a header "Current Quality of Life". Below the header is the question: "How do you feel about your current quality of life as it relates to your overall health?". There are six radio button options: "Delighted", "Satisfied", "Mixed", "Dissatisfied", "Terrible", and "Rather be dead". The "Satisfied" option is selected, indicated by a purple square next to the radio button. At the bottom of the window are two buttons: "Go Back" on the left and "Continue" on the right.

2. Patient will read and then select their choice;
3. Hit continue;

4. Patient will read and then hit continue. Questions may be answered by research assistant;

Interview

[figure not shown]
YOUR CURRENT HEALTH CONDITION

The next several screens will ask about trades you would make to completely cure your current health condition (including your wounds). Each trade will ask you to choose between living the rest of your life in your current health condition, or taking a treatment that cures all of your health problems but shortens your life by some amount.

This is a test to see how you feel. It is not a test to see what you know. Your private results will not be shown to anyone. When it is too hard to choose between the treatment or no treatment then simply click on the “It is too hard to choose” box.

Go Back Continue

5. Patient will read, ask questions to research assistant if necessary and then choose yes or no;
6. If they hit yes then they will go on to trade questions;
7. If no, then patient will go to next section focusing on their wound and not their general health;
8. Either way they hit continue;

Please consider this IMAGINARY CURE for all your health problems (including your wound)

We are now interested in YOUR CURRENT HEALTH CONDITION and your preferences for living with it for a long time or shortening your life but living in perfect health. Remember, we do not know how long you have to live.

Imagine a cure that makes people completely well.
People who take the cure have no health problems and no wounds.

The cure has just one snag: it shortens life expectancy.
This means that most patients will not live as long as they expected to live,
but during their shorter life they will be perfectly healthy. They will not have wounds.

Please IMAGINE that without a cure YOU have 5 years to live in YOUR CURRENT HEALTH CONDITION (including your wound). Would you give up even a day of those 5 years to be completely cured of all health problems?

Yes
 No

Go Back Continue

9. Assuming they choose yes, the patient will click on the box of their preference. In this scenario the patient may choose “No treatment” which indicates they would rather live 5 years in their current overall health condition including their wounds rather than live 4 years completely cured of all health problems but die 1 year early (The screen will transition to new scenario - goto next page);

The screenshot shows a software window titled "Interview" with a grey background. At the top, the text "Your Current Condition" is centered in bold. Below it, the question "Which of these choices would you prefer?" is centered. There are three main choice boxes: "Treatment" (Live 4 years completely cured of all health problems but die 1 year early), "No treatment" (Live 5 years with my current overall health condition, including my wounds), and "Choice C" (It is hard to choose). At the bottom, there are three buttons: "Go Back", "Start Over", and "Skip" (with an unchecked checkbox).

Interview

Your Current Condition

Which of these choices would you prefer?

Treatment

Live 4 years completely cured of all health problems but die 1 year early

No treatment

Live 5 years with my current overall health condition, including my wounds

Choice C

It is hard to choose

Go Back

Start Over

Skip

10. The trade questions continue after the patient chooses “No treatment”. A new scenario evolves whereby the patient will make another choice. For sake of demonstration the patient selects “Treatment”. Their preference is 2 years completely cured of all health problems but die 3 years early over “No treatment”. A new screen comes forward (next page);

The screenshot shows a window titled "Interview" with a grey background. At the top, it says "Your Current Condition" and "Which of these choices would you prefer?". There are three choice boxes: "Treatment" (Live 2 years completely cured of all health problems but die 3 years early), "No treatment" (Live 5 years with my current overall health condition, including my wounds), and "Choice C" (It is hard to choose). At the bottom, there are buttons for "Go Back", "Start Over", and "Skip" (with an unchecked checkbox).

Interview

Your Current Condition

Which of these choices would you prefer?

Treatment

Live 2 years completely cured of all health problems but die 3 years early

No treatment

Live 5 years with my current overall health condition, including my wounds

Choice C

It is hard to choose

Go Back

Start Over

Skip

11. The trade continues until patient cannot decide between Treatment or No treatment. They click on Choice C which is hard to choose. This trade is done for general health but with a wound. A new screen will will evolve (next page);

The screenshot shows a window titled "Interview" with the following content:

Your Current Condition
Which of these choices would you prefer?

Treatment
Live 4 years, 11 months completely cured of all health problems but die 1 month early

[figure not shown]
No treatment
Live 5 years with my current overall health condition, including my wounds

Choice C
It is hard to choose

Go Back Start Over
 Skip

[figure not shown]
12. Status of interview;

13. Hit continue to go to wound focus;

14. Patient answers question related to their wound;

15. Hit continue;

The screenshot shows a window titled "Interview" with a subtitle "Quality of Life as related to your wounds". The main question is "How do you feel about your current quality of life as it relates to your wounds?". There are six radio button options: "Delighted", "Satisfied", "Mixed", "Dissatisfied", "Terrible", and "Rather be dead". The "Dissatisfied" option is selected and highlighted with a purple background. At the bottom, there are two buttons: "Go Back" on the left and "Continue" on the right.

Interview

Quality of Life as related to your wounds

How do you feel about your current quality of life as it relates to your wounds?

Delighted

Satisfied

Mixed

Dissatisfied

Terrible

[figure not shown]
Rather be dead

Go Back

[figure not shown]
Continue

16. Patient will read the text;

17. Hit continue;

18. Patient will read and choose either yes or no. If no then this trade stops and goes into ricky treatment section;
19. Check yes it will go to trade section where patient will choose preferences again;
20. Hit continue either way;

The screenshot shows a window titled "Interview" with a header "Your Current Wounds". The text inside the window reads: "A wound can cause quite a bit of pain and difficulty in getting about. Imagine a cure for all wounds. It heals wounds right away, and the wounds do not come back. People who take the cure have no wounds. They have no wound pain and no wounds to stop them from doing things. This cure does not treat other health problems. The cure has just one snag: it shortens life expectancy. This means that most patients will not live as long as they expected to live, but during their shorter life they will have no wounds or wound pain, and able to move around just as they want. Please imagine that without a cure YOU have 5 years to live with YOUR CURRENT WOUND and your other health problems. Would you give up even a day to cure your wounds? This cure would not change your other health problems at all." Below the text are two radio buttons: "Yes" (selected) and "No". At the bottom are two buttons: "Go Back" and "Continue".

21. Patient will select their preferences related to their wound. Screens will change based on their selection;

The screenshot shows a window titled "Interview" with the following content:

Your Current Wounds

Which of these choices would you prefer?
Remember that treatment cures only your wounds.

Treatment

Live 4 years
in my current condition,
but completely cured of my wounds,
but die 1 year early

No treatment

Live 5 years
with my current health condition,
including my wounds

Choice C

[figure not shown]
It is hard to choose

Go Back

Start Over

[figure not shown]
Skip

22. Another example of screen change. If they click on Choice C then this trade is done (Next screen);

[figure not shown]
23. Status of interview;

24. Hit continue;

[figure not shown]

25. The next set of trades require a basic understanding of survival curves. This one slide gives a general overview that is enough to complete next sections of trades. The research assistant can also guide the patient here;

[figure not shown]
26. Hit continue after review;

27. This section focuses on risky treatment that may decrease early survival but if they survive their prognosis for longer survival becomes better. In the example below, the patient will most likely choose the green box as it gives better probability of survival over 5 years. Once they select their preference the trades begin – go to next page;

28. Notice that the survival curve changes with their selection in previous section. Patient now will most likely click on option B. Page transitions to next preference trade – go to next page;

29. The scenario changes in this section with new trade preference options. Also notice the survival curve changes based on choices. Patient selects Option B and a new trade appears on next page;

Interview

Trade-offs between early survival and late survival

Imagine that you are in *your current condition*. Your survival curve is the black dashed line. The green curve shows that the risky treatment in option A decreases early survival, but late survival is better. It will not change your wound problems. Look at the curves, read the options, and choose A, B, or C by clicking on its box. The green curve will shift after each choice.

Option A

Take the treatment risk
have a 56% chance
to live 5 years in my current
condition.

Time in years	Current Condition (Black Dashed)	Option A (Green Solid)
0	100%	100%
1	~95%	~70%
2	~90%	~68%
4	~80%	~60%
6	~65%	~45%
8	~45%	~25%
10	~15%	~15%

Option B

Do not take the treatment risk,
have a 71% chance
to live 5 years in my current
condition

Option C

It is hard to choose

Go Back
Continue

30. Choose Option B. New section comes open on next page. Survival curve changes with selections;

Interview

Trade-offs between early survival and late survival

Imagine that you are in *your current condition*. Your survival curve is the black dashed line. The green curve shows that the risky treatment in option A decreases early survival, but late survival is better. It will not change your wound problems. Look at the curves, read the options, and choose A, B, or C by clicking on its box. The green curve will shift after each choice.

Option A

Take the treatment risk
have a 66% chance
to live 5 years in my current
condition.

Time in years	Current Condition (Black Dashed)	Option A (Green Solid)
0	100%	100%
1	95%	80%
2	90%	78%
4	75%	70%
6	55%	55%
8	35%	35%
10	10%	25%

Option B

Do not take the treatment risk,
have a 71% chance
to live 5 years in my current
condition

Go Back

It is hard to choose

Continue

31. Patient chooses Option C and the trade stops. Next section automatically appears;

Interview

Trade-offs between early survival and late survival

Imagine that you are in *your current condition*. Your survival curve is the black dashed line. The green curve shows that the risky treatment in option A decreases early survival, but late survival is better. It will not change your wound problems. Look at the curves, read the options, and choose A, B, or C by clicking on its box. The green curve will shift after each choice.

Option A

Take the treatment risk
have a 71% chance
to live 5 years in my current
condition.

Time in years	Current Condition (Black Dashed)	Option A (Green Solid)
0	100%	100%
1	~95%	~85%
2	~90%	~82%
4	~75%	~75%
6	~55%	~65%
8	~35%	~45%
10	~15%	~25%

Option B

Do not take the treatment risk,
have a 71% chance
to live 5 years in my current
condition

Option C

[figure not shown]
It is hard to choose

Go Back

[figure not shown]
Continue

32. Status page;

33. Hit continue;

[figure not shown]

34. The next section is similar to the previous risky treatment scenario except it focuses on wounds only. Patient will select accordingly until they hit Option C when the survey is over. The next section gives quality of life utility measurements with discounted numbers;

[figure not shown]
35. This screen shows current health condition utility measure between 0 and 1 (0.77). A discounted rate of 0.07 was subtracted from the utility measure giving the above answer 0.77.

36. Hit continue;

37. Wound quality of life utility measurement that is discounted;

38. Hit continue;

- 39. The interview is complete;
- 40. The researcher can save and quit or do another interview.

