19.4 DISCRETE EVENT SIMULATION MODEL TO MEASURE COST-EFFECTIVENESS AND COST-BENEFIT

A discrete event simulation model (see figure this page) is used to measure the costs (e.g., clinical human resources, medical supplies, drugs, diagnostics, investigations and CelluTome) and consequences (e.g., healing, clinical infection, hospitalization and death) over the course of the study time period from the perspective of the hospital/outpatient, payer and patient. The model will contain health states (e.g., healed ulcer, infected ulcer, severely infected ulcer, hospitalization (e.g., cellulitis, amputation), uncomplicated ulcer and death). The patient and respective ulcer will travel over time in the model for three years accumulating costs and consequences. Cost analysis for differing perspectives and time-horizons are completed using the advantages of the model framework.

In particular, average quality of life utility score values will be assigned to

CELLUTOME™ IN VENOUS LEG

each health state from the use of Wound-Trade©, time trade-off assessment (Appendix 19.2) matched to the health states in a separate matching analysis between scores and health state of the ulcer/patient measured in the case report form. As the patient/ulcer traverses through the model over time weekly assigned utility values in each health state will be compiled and totaled for each patient and respective group at years end. This will facilitate the determination of cost per quality adjusted life year comparison between groups.

A cost-benefit (return-on-investment) measurement will also be completed from the hospital/outpatient perspective to show value to the institution. Average direct medical costs attributed to resource utilization, medical supplies, drugs, diagnostics and CelluTome™ will be estimated during the trial for each group. Financial benefits include averted costs of complications from rapid healing that may be consequential to the hospital/outpatient clinic.

Cost-effectiveness is used to demonstrate the value of CelluTome™ for rapid healing, reduced complications and therefore reduced financial impact for the payer.

Return-on Investment Metrics:

Metric	Definition	Formula
Costs	Total amount of money spent on new improvement process	$= \sum_{i=1}^n \text{Cost}_i$
Benefits	Total amount of money gained from a new and improved process	$= \sum_{i=1}^n \text{Benefit}_i$

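### Appendix 19.2 describes discounting a time trade-off utility by subtracting 0.07 from it, which lowers a score that discounting would raise; the scoring rule, and the score that enters the cost-utility model, need to be stated correctly.

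*Combined protocol and SAP*

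**What the plan says.** Appendix 19.2 sets the utility scale: "Utility values measure the preference for a health state and range from 0.0 (death) to 1.0 (perfect health"). It then defines the time trade-off index as x/y, where x healthy years are judged equal to y years with the condition. In its example, 15 healthy years against 20 years with a wound, "this individual is giving a chronic wound a health utility index of 0.75".

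The only general statement about discounting is that the software "enables a discounted, risk-adjusted, quality of life health utility index score through classic time-trade-off methodology". No formula, rate or source follows. The interview uses a 5-year horizon: "Please IMAGINE that without a cure YOU have 5 years to live in YOUR CURRENT HEALTH CONDITION (including your wound").

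At the end of the walkthrough, step 35 describes the general-health result screen: "A discounted rate of 0.07 was subtracted from the utility measure giving the above answer 0.77". Step 37 says that the wound score is discounted too, but gives no amount.

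Appendix 19.4 feeds these scores into a three-year simulation: "average quality of life utility score values will be assigned to" each health state, and the weekly values are added up to obtain cost per QALY. It does not say whether the raw or the discounted score is used, or whether QALYs are discounted in the model. Cost-effectiveness is a secondary outcome in Section 3.

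**The concern.** A discount rate applies per unit of time to a stream of years. It cannot sensibly be subtracted from a ratio of years. Appendix 19.4 itself uses the usual form for money: its net present value divides benefits by one plus a rate, raised to the number of years.

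The direction is also wrong. The years a subject gives up lie at the end of the horizon, so discounting makes them count for less and the utility goes up. Subtraction takes it down. As a rule for all subjects, subtraction would also move the top of the scale away from the stated anchor.

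At stake are the health-state utilities behind cost per QALY, and the risk of reducing the same years twice if the model later discounts QALYs as well.

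**Working it through.** **Inputs.** From Appendix 19.2: 0.07 subtracted, 0.77 displayed, horizon y = 5 years, worked example x = 15 and y = 20, anchors 0 and 1. From Appendix 19.4: model horizon 3 years. Reading 0.07 as 7% per year is an assumption.

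**1. The plan's own figures.** The x/y example reproduces: 15/20 = 0.75. The 0.77 cannot be reproduced from a documented raw score.
- Literal subtraction needs a raw score of 0.77 + 0.07 = 0.84, which appears nowhere.
- A multiplicative reading needs 0.77/0.93 = 0.828.
- Present-value discounting at 7% over 5 years needs about 0.74.
- The one general-health trade shown to its end ("Live 4 years, 11 months completely cured of all health problems but die 1 month early") gives 59/60 = 0.983, or 0.913 after subtraction.

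So 0.77 is neither confirmed nor refuted, and 0.84 below is back-solved.

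**2. Direction.** A discounted time trade-off utility is PV(x)/PV(y) = [1 − (1+r)^−x] / [1 − (1+r)^−y]. PV is concave and zero at zero, so for r > 0 and x < y this ratio always exceeds x/y. With x = 0.84 × 5 = 4.2, y = 5 and r = 0.07:

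(1 − 1.07^−4.2) / (1 − 1.07^−5) = 0.2474 / 0.2870 = 0.862

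The continuous form gives 0.863. Over rates of 1% to 10% it runs from 0.843 to 0.872. Even a negative rate of −7% lowers the score only to 0.816, not to 0.77.

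| Case | Raw x/y | Raw − 0.07 | PV ratio at 7% (annual) |
|---|---|---|---|
| Implied raw score, y = 5 | 0.84 | 0.77 | 0.862 |
| Appendix example, 15/20 | 0.75 | 0.68 | 0.860 |
| Top of scale | 1.00 | 0.93 | 1.00 |
| Bottom of scale | 0.00 | −0.07 | 0.00 |

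**3. Effect on QALYs, if every subject's score is reduced by 0.07 and the reduced scores enter the model.**
- Absolute QALYs: 0.07 × 3 = 0.21 lost per subject alive for three years; 0.07 × 12/52 = 0.016 over 12 weeks.
- Survival difference: death stays at 0, so each extra life-year is undervalued by 0.07.
- Two living states, equal survival: with assumed raw utilities of 0.90 and 0.60, (0.90 − 0.07) − (0.60 − 0.07) = 0.30, the same as on the raw scale.
- Unequal shift: if healed were fixed at 1.0 (an assumption) and only the unhealed state reduced, the gap at raw 0.84 grows from 0.16 to 0.23, or 44%.

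**The case against.** The strongest reply is that step 35 explains a demonstration screen and does not specify the scoring. The algorithm is not in the documents. Survival-curve trades precede the result screens, so 0.07 could be a fixed annual rate, a rate elicited from that one subject, or the size of that subject's adjustment. The sentence may simply misdescribe a sound calculation. This stands, and it makes every figure for QALYs conditional. It does not remove the point, because this sentence is the plan's only account of how the discounting is done.

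The 0.93 ceiling is conditional too. A subject who would give up no time skips the trade, and the appendix does not say how that subject is scored.

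Three stronger readings are tempting and are not supported:
- *That scores leave the 0 to 1 scale.* The displayed 0.77 is within range, and a negative value needs a raw score below 0.07. What subtraction breaks is the anchor at the top.
- *That the QALY gain from healing is overstated by some 10% to 16%.* That excess appears only against present-value utilities and for assumed pairs of scores. Against raw x/y the gap is unchanged. At low utilities the sign reverses: 2 versus 1 year out of 5 is a gap of 0.200 after subtraction and 0.213 when discounted at 7%.
- *That the trial's QALYs are therefore wrong, or discounted twice.* Appendix 19.4 does not say which score enters the model and specifies no discounting of QALYs.

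**Conclusion.** The scoring step as written is not discounting and moves the utility the wrong way for any positive rate: 0.77 instead of about 0.86 for the implied raw score of 0.84, a difference of about 0.09. Applied to every subject, it would put perfect health at 0.93 instead of 1.0.

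Whether this reaches the results depends on the unseen algorithm and on which score the model uses. If subtracted scores are used, absolute QALYs and the value of survival differences are understated by 0.07 per life-year. Comparisons between living states with equal survival are unaffected relative to the raw scale, unless states are shifted unequally. Equal treatment is not assured, because no amount is given for the wound score.

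The assumptions are positive time preference, 0.07 as an annual rate for the comparison, and a constant 0.07 for the QALY effects. Cost-effectiveness is secondary and has no hypothesis among H1 to H8 in Section 9.2; the primary time-to-heal analysis is not touched. Priority is low to moderate.

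**What to change.** In Appendix 19.2, remove the subtraction. State that raw x/y is the health-state utility for both the general-health and the wound score, and say how subjects who decline to trade any time are scored. In Appendix 19.4, say which of the two scores is assigned to the health states, and apply any discounting of QALYs and costs once, inside the simulation, at a stated rate.

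If a discounted time trade-off is preferred, write PV(x)/PV(y) with its rate and source, and do not discount those years again. If the software already does this, correct the sentence in step 35.

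The cost is appendix wording, plus recomputing saved scores where the indifference points were retained. The documents do not say whether they are, so this should be checked with the software's developers before further interviews are scored. Where they were kept, no new data are needed.
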